9.1.2 Patient questionnaire

The patient questionnaire can be found in [Appendix 1](#).

The patient questionnaire is relating to VVC symptoms (itching, burning, and irritation) and pessary administration. Questionnaire should be filled in via the mobile application ViedocMe™ (see [Section 11.1.2](#)) on Days 0 to 6, Day 11 and Day 25.

Questions about usability should be filled in by all patients on Day 6.

^a scoring scale:

0 = none (absent)

1 = mild (slight)

2 = moderate (definitely present)

3 = severe (marked, intense)

10 SAFETY AND TOLERABILITY ASSESSMENTS

Assessments described in [Section 10.1](#), will be used to assess the secondary endpoints 7, 8, and 9 (see [Section 4.2.1](#)) and the two exploratory endpoint (see [Section 4.3.1](#)).

Assessments described in [Section 10.2](#), AEs will be used to assess the secondary endpoint 1 (see [Section 4.2.1](#)).

10.1 Clinical laboratory evaluation

10.1.1 Vaginal swab samples

Vaginal samples will be collected via a vaginal swab by the Investigator or delegatee on site visits (Day 0, Day 7 and Day 14) or by patients themselves at home, on Day 25. For the testing made at home, labelled swabs will be given to the women who then will do the testing as per provided instructions. The swabs for vaginal culture will need to be sent for analysis to ensure receipt by the lab within 48 hours. Swabs for sequencing of the vaginal microbiome can be stored in ambient temperature for a month. These samples will be gathered and stored in < -70°C until analysis at the end of the study.

The collected samples will be used for the following analyses.

- **Microscopic analysis; presence of hyphae:** KOH or saline preparations for fungus, using samples collected on Day 0, Day 7 and Day 14. Briefly, vaginal samples will be covered with 10% to 20% KOH or 0.9% isotonic NaCl solution and inspected under a microscope. Presence of hyphae indicates *Candida* and will serve as an immediate, preliminary VVC diagnosis.
- **Candida culture:** Samples collected on Days 0, 7, 14 and 25, will be sent to laboratory for culture and confirmation of the VVC diagnosis/mycological cure.
- **Sequencing of the vaginal microbiome:** Vaginal swabs for sequencing of the vaginal microbiome will be collected on Days 0, 7, 14, and 25. On Days 0 and 7, the swabs will be taken in duplicates.

The effects of the investigational product on the vaginal microbiome will be assessed. Collected samples will be sent to a central laboratory for assessment of bacterial and fungus species, through DNA sequencing.

Samples sent to the central laboratories will be coded with no possibility to identify the patients, and all samples will be destroyed directly after the analysis has been completed. Samples that are analysed at the investigational site will be destroyed directly after analysis. No samples will be kept for future research.

10.1.2 Vaginal pH

Patients' vaginal pH will be assessed on Day 0 and on Day 7 by the Investigator or delegatee using a pH-test strip.

Vaginal pH will be used for assessments of investigational product *in vivo* duration. If the vaginal pH on Day 7 is lower than the pH on Day 0, that would indicate appropriate release duration.

10.2 Untoward medical events and AEs

10.2.1 Adverse event

An AE is any untoward medical occurrence, unintended disease or injury, or any untoward clinical signs including abnormal laboratory findings in patients, users or other persons, in the context of a clinical investigation, whether or not related to the investigational device.

Note:

- a. This definition includes events that are anticipated as well as unanticipated events.
- b. This definition includes events occurring in the context of a clinical investigation-related to the investigational device, the comparator or the procedures involved.

10.2.2 Adverse device effect

An adverse device effect (ADE) is an AE related to the use of an investigational medical device.

NOTE 1 This includes any AE resulting from insufficiencies or inadequacies in the instructions for use, the deployment, the implantation, the installation, the operation, or any malfunction of the investigational medical device.

NOTE 2 This includes any event that is a result of a use error or intentional abnormal use of the investigational medical device.

The following events are not considered untoward medical events/AEs:

- Medical interventions planned before study initiation given that the status of the participant has not worsened since signing the consent form or the intervention has had to be done at an earlier date.
- Conditions or diseases known when the patient signs the ICF, are not considered untoward medical events AEs. These will be registered in the medical history eCRF page.

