3.3.2 Clinical data

The Gedea Pessary (*p*Hyph gen II) used in this clinical investigation has been tested in a randomised, double-blind, placebo-controlled investigation in adult women with BV, the CL3 study. The objective of the investigation was to evaluate clinical performance, and safety of initial and preventive treatment with the Gedea Pessary, as compared to placebo, in women with BV. In the part 1 of the study, treatment for 6 consecutive days was given and the clinical cure rate on Day 7, defined as absence of all of the 3 Amsel criteria was evaluated (pH excluded). 115 patients treated with *p*Hyph and 30 patients treated with placebo were included in the Full Analysis Set (FAS). There were no significant between-group differences in the percentage of women who were clinically cured; 50.4% in the *p*Hyph group and 46.7% in the placebo group. *In vitro* studies performed, showed that the placebo was not inactive, it strongly promoted the growth of *Lactobacillus Iners* and this may explain the high placebo cure rate in the CL3 study⁵⁸.

During Part 1 of the CL3 study, 26 AEs were reported by 22 patients (19.1%) in the Gedea Pessary group and 5 AEs were reported by 4 patients (13.3%) in the placebo group. The most commonly reported AEs were Vulvovaginal candidiasis (Gedea Pessary: 5 AEs in 5 patients, 4.3%; Placebo: 1 AE in 1 patient, 3.3%), Vulvovaginal burning sensation (Gedea Pessary: 3 AEs in 3 patients, 2.6%) and Vulvovaginal pruritus (Gedea Pessary: 2 AEs in 2 patients, 1.7%; Placebo: 1 AE in 1 patient, 3.3%).

A total of 8 AEs (Vulvovaginal discomfort [2 events in 2 patients], Dysmenorrhoea, Vulvovaginal pruritus, and Vaginal discharge/Vulvovaginal burning sensation/Vulvovaginal erythema/Vulvovaginal swelling [reported at the same time in 1 patient]) in 4 patients (2.8%, N=145) (Gedea Pessary: 6 AEs in 3 patients, 2.6%; Placebo: 2 AEs in 1 patient, 3.3%) were judged as possibly related. One AE (Vulvovaginal pruritus) in 1 patient (0.9%) in the Gedea

Pessary group was judged as probably related to the study procedure. Most AEs (22 AEs) were of mild intensity, except for 9 AEs (Vulvovaginal candidiasis [2 events], Back pain, COVID-19, Urinary tract infection, and Vaginal discharge/Vulvovaginal burning sensation/ Vulvovaginal erythema/Vulvovaginal swelling [reported at the same time in 1 patient]) in 6 patients (4.1%) that were assessed as moderate. No severe events were reported.

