6.2 Recruitment

Post-menarchal, pre-menopausal females, 18 years or older, seeking care for VVC symptoms (itching, burning, or irritation) should be considered. Patients with confirmed VVC, may be informed verbally and in writing about the study and asked about their willingness to participate (clinical routine samples and gynaecological examination may be used for confirmation of the VVC diagnosis).

Patients may also be pre-informed about the study by the use of advertisement through social media; these patients will directly book appointments with the clinic.

After signing of the ICF, the screening procedures may start and available clinical routine samples may be used for confirmation of VVC diagnosis).

Patients who have signed the ICF shall be listed on a Screening and enrolment log together with an assigned Screening number. Patients not fulfilling *all* inclusion criteria as described in [Section 6.3](#), or fulfilling *any* of the exclusion criteria listed in [Section 6.4](#), shall be considered Screening failures. Screening failure reasons shall be stated in the Screening enrolment log, and recorded in the eCRF.

The patient should not be enrolled, or the enrolment should be postponed, if menstruation is foreseen to occur at the time of the Day 7 visit.

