10.2.3 Serious Adverse Events

A SAE is an AE that led to any of the following:

- a) Death,
- b) Serious deterioration in the health of the subject that resulted in any of the following:
 - Life-threatening illness or injury
 - Permanent impairment of a body structure or a body function
 - Hospitalisation or prolongation of patient hospitalisation
 - Medical or surgical intervention to prevent life-threatening illness or injury or permanent impairment to a body structure or a body function
 - Chronic disease
- c) Foetal distress, foetal death or a congenital physical or mental impairment or birth defect.

NOTE: Planned hospitalisation for a pre-existing condition, or a procedure required by the current CIP, without serious deterioration in health during the course of the study, is not considered an SAE.

A serious adverse device effect (SADE) is an ADE that has resulted in any of the consequences characteristic of a SAE.

An unanticipated serious adverse device effect (USADE) is a SADE, which by its nature, incidence, severity, or outcome has not been identified in the current version of the risk analysis report.

An anticipated serious adverse device effect (ASADE) is an effect, which by its nature, incidence, severity, or outcome has been identified in the risk analysis report.

SAEs related to procedures imposed by the CIP but not with the use of the device should not be considered Serious Adverse Device Effects.

The classification of an untoward medical event as USADE or ASADE will be done retrospectively. The event will initially be captured as an SAE.

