7.9.3 Secondary Performance Variables

All secondary clinical performance endpoints will be presented with descriptive statistics. The following binary secondary clinical performance endpoints will show the endpoint estimate together with a two-sided 95% CI based on the Wilson score.

- Proportion of patients having a continued clinical response to treatment at Day 25, defined as the proportion of patients clinically cured on Day 7-14 (taking into account the intercurrent events and applying the composite strategy as described in Section 7.9.1) and thereafter responding "no" to the yes/no question, "Have the symptoms recurred?" and no rescue medication has been given up to day 25
- Proportion of patients having a cure defined as clinical cure Day 7-14 according to primary endpoint (taking into account the intercurrent events and applying the composite strategy as described in Section 7.9.1) and mycological cure at Day 7-14 (culture negative for growth of Candida species).
- Proportion of patients having a reduction in CVVS score on Day 7-14 compared to Day 0.
- Proportion of patients having a reduction in the sum of the 3 vulvovaginal symptoms scores (itching, burning, and irritation) on Days 1 to 7, Day 11, Day 14 and Day 25, compared to Day 0.
- Proportion of patients having a mycological cure as assessed by vaginal culture on Day 7-14 and Day 25.
- Proportion of patients having an absence of Candida hyphae in the wet smear on Day 7-14.

Statistical Analysis Plan

Study ID: CL4

Presentation of the continuous secondary clinical performance endpoints below will include the two-sided 95% CIs for the arithmetic mean.

- The change in CVVS score from Day 0 to Day 7-14 (last available assessment).
- Change in the sum of the 3 vulvovaginal symptoms scores (itching, burning, and irritation) to each post baseline assessment.

Usability will be measured on Day 6, by a patient questionnaire (see Appendix 1). The questionnaire contains 2 yes/no (i.e. binary) variables, 2 categorical variables and the question, "How do you generally regard the treatment?", rated on a 1-10 integer scale. These endpoints will be presented descriptively, treating the question rated on the 1-10 scale as a continuous variable. In case of multiple assessments of usability, the first non-missing value will be used.

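### The protocol's AE exclusion for conditions known at consent has no worsening clause, so on-treatment aggravation of entry symptoms can be left out of the safety endpoint

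*Protocol*

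**What the plan says.** Protocol 10.2.2 lists two kinds of occurrence that are not AEs. Planned medical interventions are excluded "given that the status of the participant has not worsened since signing the consent form" (or the intervention has had to be brought forward). The second item reads "Conditions or diseases known when the patient signs the ICF, are not considered untoward medical events AEs", and continues "These will be registered in the medical history eCRF page". It carries no condition about worsening.

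The general definition in Protocol 10.2.1 begins "An AE is any untoward medical occurrence, unintended disease or injury, or any untoward clinical signs" and does not mention aggravation of something already present. Protocol 10.2.5 has staff ask about health problems and device-related events at each contact, and allows examination findings to generate AEs.

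On the population, Protocol 6.2 says that women "seeking care for VVC symptoms (itching, burning, or irritation) should be considered". Inclusion criterion 3 in Protocol 6.3 adds a white or creamy discharge and at least two of six signs and symptoms of at least moderate grade.

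Secondary endpoint 1 (Protocol 4.2.1) is safety and tolerability based on reported treatment-emergent AEs. SAP 7.9.4 tabulates AEs by class, term, severity and causality, but defines neither treatment-emergent nor worsening. The 0-3 symptom scores are analysed as performance in SAP 7.9.3, including "Change in the sum of the 3 vulvovaginal symptoms scores (itching, burning, and irritation) to each post baseline assessment".

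**The concern.** The exclusion is usually harmless because the study disease and the product's likely side effects differ. Here they overlap. A woman who enters with mild burning and has severe burning after the first pessaries has a condition that was known at consent. Under the literal rule it stays on the medical history page and is not an AE. Since Protocol 10.2.2 defines an adverse device effect as a kind of AE, it cannot become a device effect either, and it receives no severity or causality rating.

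The same woman may then appear only as a treatment failure: rescue treatment and discontinuation for lack of performance are handled as intercurrent events of the cure endpoint (Protocol 12.4.2). Local intolerance and non-response become hard to tell apart. At stake is whether the AE tables can show how daily dosing is tolerated on already inflamed mucosa.

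**Working it through.** The plan gives no figure on this point, so the check sets the texts side by side and adds a few counts.

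**1. Is a worsening clause supplied elsewhere?**
- Protocol 10.2.2, first item: a clause is present, for planned interventions only.
- Protocol 10.2.2, second item: none.
- Protocol 10.2.1: general definition, silent on worsening.
- Protocol 10.2.3: the deterioration wording concerns "Planned hospitalisation for a pre-existing condition, or a procedure required by the current CIP, without serious deterioration in health". It limits what counts as serious and does not qualify the AE exclusion.
- Protocol 8.5 and 10.2.5: events between consent and first dose go to the medical history log. Nothing is said about later aggravation.
- SAP 7.9.4: no rule.

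No other text supplies the clause.

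**2. Does every woman enter with an overlapping complaint?** Criterion 3 can be met by any of 6 × 5 / 2 = 15 pairs of features. Three pairs contain signs only (oedema/erythema, oedema/excoriation, erythema/excoriation). So the criterion alone does not force a symptom at entry; the recruitment text does, and it needs only one of the three. Discharge is required of all.

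**3. What did the earlier study of this formulation show?** Protocol 3.3.2 reports Part 1 of CL3, in bacterial vaginosis, with 115 women on the pessary and 30 on placebo. Among the commonest AEs was "Vulvovaginal burning sensation (Gedea Pessary: 3 AEs in 3 patients, 2.6" per cent of that arm (3/115 = 2.6%). Related AEs over both arms:
- possibly related: discomfort 2 + dysmenorrhoea 1 + pruritus 1 + four terms reported together by one patient (discharge, burning, erythema, swelling) = 8;
- probably related, to the study procedure: pruritus 1;
- total 8 + 1 = 9, of which 9 − 1 = 8 were local.

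Six of these 8 match a CL4 entry feature directly (pruritus 2, discharge, burning, erythema, swelling). The two discomfort events overlap more loosely, with irritation.

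By arm, the 8 possibly related AEs split into 6 in 3 pessary patients and 2 in 1 placebo patient. The patient with four terms must be on the pessary, because placebo had only 2. In the pessary arm, 3 patients had a possibly related AE and 1 a probably related one, so 3 or 4 women: 3/115 = 2.6% to 4/115 = 3.5%. Applied to 26 women this is 26 × 0.026 = 0.7 to 26 × 0.035 = 0.9 women. One affected woman in CL4 is 1/26 = 3.8%, so a single unrecorded case changes the profile.

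**4. Do the performance tables recover it?** In part. SAP 7.1.1 requires the maximum as well as the mean, plus individual listings, so net worsening of one woman's symptom sum appears as a positive maximum on that day. Two things are lost from the tables. First, offset between items: if burning goes from 1 to 3, itching from 3 to 1 and irritation is unchanged, the change in the sum is +2 − 2 + 0 = 0. Second, the proportion with a reduction pools unchanged with worse. None of this output is presented as safety.

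**The case against.** The strongest reply is that the text is silent on worsening and does not name it as excluded. The known condition is the infection; a reaction to the pessary can be seen as a separate event under 10.2.1, and 10.2.5 asks directly about device-related events. An investigator may therefore report it. This stands, and it rules out the reading that such worsening can never be an AE. What remains is that reporting depends on how each site reads two passages that pull in different directions, in a multi-centre study of 26 women.

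A reader might also infer that the trial would show a clean local profile whatever happened. The documents do not support that. Burning that is new in a woman who entered with itching alone was not present at consent and is still captured, and net worsening can be seen in the maximum change and the listings.

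Nor do the CL3 counts show that most related events would be suppressed. They pool both arms, four local terms come from one patient, and the expected number in 26 women is below one. The documents give neither baseline symptoms in CL3 nor its AE rule, so one cannot say that its burning and pruritus were new symptoms. In CL1, 22 women with candidiasis were evaluated after the earlier formulation and few AEs were reported (Protocol 3.3.2). That is mildly reassuring, but its schedule differed and its AE rule is not stated.

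**Conclusion.** The point holds as a defect in a stated rule. Protocol 10.2.2 omits, for known conditions, the worsening limit that it applies to planned interventions, and nothing else in the documents supplies it. Secondary endpoint 1 can therefore under-count aggravation of symptoms or signs present at entry, and such events can go without a causality rating.

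The size of the under-count cannot be derived. It depends on how sites read the rule and on how often the product aggravates existing symptoms, and the CL3 rates come from a different disease. The conclusion rests on the literal wording and on recruitment following Protocol 6.2. It does not extend to new symptoms. The matter should be fixed but is not critical: safety here is a descriptive secondary endpoint and the primary cure-rate analysis does not depend on it.

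**What to change.** **Protocol 10.2.2, second item.** Add: *unless the condition worsens in severity or frequency after the first administration, in which case the worsening is recorded as an AE with causality assessed*.

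**SAP 7.9.4.** Add a descriptive tolerability table giving:
- the number of women whose itching, burning or irritation score on any of Days 1-6 exceeds the pre-treatment score, by item and by 1 or by 2 or more points;
- the number whose erythema, oedema or excoriation score at Day 7 exceeds Day 0.

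The pre-treatment symptom score should be the Day 0 visit score recorded in the eCRF (SAP 6.4). SAP 7.1.2 starts the treatment period at 18:00 on the screening day, and the app reminder in Protocol Appendix 1 pairs scoring with bedtime dosing, so the Day 0 app score may fall after baseline. The visit score is taken by interview and the later ones by app; a footnote should say so.

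**Cost.** One sentence and one table, with no new data. Some natural worsening of the disease will be counted as AEs; the causality rating helps to separate it. The protocol change needs approval under Protocol 13.5. The last visit was planned for Q4 2023 (Protocol 13.7) and the SAP was signed in March 2024. If follow-up is complete, the clause can no longer change what was captured. The table can still be added as a documented change in SAP 7.10, and the clinical investigation report should state the limitation in AE capture.

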10.2.3 Serious Adverse Events

A SAE is an AE that led to any of the following:

- a) Death,
- b) Serious deterioration in the health of the subject that resulted in any of the following:
 - Life-threatening illness or injury
 - Permanent impairment of a body structure or a body function
 - Hospitalisation or prolongation of patient hospitalisation
 - Medical or surgical intervention to prevent life-threatening illness or injury or permanent impairment to a body structure or a body function
 - Chronic disease
- c) Foetal distress, foetal death or a congenital physical or mental impairment or birth defect.

NOTE: Planned hospitalisation for a pre-existing condition, or a procedure required by the current CIP, without serious deterioration in health during the course of the study, is not considered an SAE.

A serious adverse device effect (SADE) is an ADE that has resulted in any of the consequences characteristic of a SAE.

An unanticipated serious adverse device effect (USADE) is a SADE, which by its nature, incidence, severity, or outcome has not been identified in the current version of the risk analysis report.

An anticipated serious adverse device effect (ASADE) is an effect, which by its nature, incidence, severity, or outcome has been identified in the risk analysis report.

SAEs related to procedures imposed by the CIP but not with the use of the device should not be considered Serious Adverse Device Effects.

The classification of an untoward medical event as USADE or ASADE will be done retrospectively. The event will initially be captured as an SAE.

10.2.4 Definitions of adverse event ratings

10.2.4.1 Severity/intensity

Untoward medical events/AEs will be rated according to their severity/intensity. The following rating will be done by the Investigator:

Mild: Transient symptoms, no interference with daily activities of the participant.

Moderate: Clear symptomatology that moderately affects the daily activities of the participant.

Severe: Symptoms that clearly affects or hinders daily activities of the participant.

10.2.4.2 Causality assessment/relatedness

The relationship between the use of the medical device^a (including the medical - surgical procedure) and the occurrence of each AE shall be assessed and categorised.^b During causality assessment activity, clinical judgement shall be used and the relevant documents, such as the IB, the CIP or the Risk Analysis Report shall be consulted, as all the foreseeable SAEs and the potential risks are listed and assessed there. The presence of confounding factors, such as concomitant medication/treatment, the natural history of the underlying disease, other concurrent illness or risk factors shall also be considered. The above considerations apply also to the SAEs occurring in the comparison group.

^a Intended as both medical device investigated in the investigation and comparator.

^b Procedure related events refers to the procedure related to the initial application of the investigational medical device only and therefore not to any other procedures or treatments applied later throughout the clinical investigation, for instance to treat AEs.

For the purpose of harmonising reports, each SAE will be classified according to 4 different levels of causality. The Sponsor and the Investigators will use the following definitions to assess the relationship of the SAE to the investigational^a medical device or procedures:

Not related: Relationship to the device, comparator or procedures can be excluded when:

- the event has no temporal relationship with the use of the investigational device, or the procedures related to application of the investigational device;
- the SAE does not follow a known response pattern to the medical device (if the response pattern is previously known) and is biologically implausible;
- the discontinuation of medical device application or the reduction of the level of activation/exposure - when clinically feasible -and reintroduction of its use (or increase of the level of activation/exposure), do not impact on the SAE;
- the event involves a body-site or an organ that cannot be affected by the device or procedure;
- the SAE can be attributed to another cause (e.g. an underlying or concurrent illness/ clinical condition, an effect of another device, drug, treatment or other risk factors);
- the event does not depend on a false result given by the investigational device used for diagnosis, when applicable;

In order to establish the non-relatedness, not all the criteria listed above might be met at the same time, depending on the type of device/procedures and the SAE.

Possible: The relationship with the use of the investigational device or comparator or the relationship with study procedures is weak but cannot be ruled out completely. Alternative causes are also possible (e.g. an underlying or concurrent illness/clinical condition or/and an effect of another device, drug or treatment). Cases where relatedness cannot be assessed or no information has been obtained should also be classified as possible.

Probable: The relationship with the use of the investigational device or comparator or the relationship with study procedures seems relevant and/or the event cannot reasonably be explained by another cause.

Causal relationship: The SAE is associated with the investigational device or comparator or with procedures beyond reasonable doubt when:

- the event is a known side effect of the product category the device belongs to or of similar devices and procedures;
- the event has a temporal relationship with investigational device use/application or procedures;
- the event involves a body-site or organ that;

^a Investigational device: any device object of the clinical investigation, including the comparators.

- the investigational device or procedures are applied to;
- the investigational device or procedures have an effect on;
- the serious event follows a known response pattern to the medical device (if the response pattern is previously known);
- the discontinuation of medical device application (or reduction of the level of activation/exposure) and reintroduction of its use (or increase of the level of activation/exposure), impact on the serious event (when clinically feasible);
- other possible causes (e.g. an underlying or concurrent illness/clinical condition or/and an effect of another device, drug or treatment) have been adequately ruled out;
- harm to the patient is due to error in use;
- the event depends on a false result given by the investigational device used for diagnosis^a, when applicable;

In order to establish the relatedness, not all the criteria listed above might be met at the same time, depending on the type of device/procedures and the serious event.

The Sponsor and the Investigators will distinguish between the SAEs related to the investigational device and those related to the procedures (any procedure specific to the clinical investigation). An AE can be related both to the procedures and the investigational device. Complications of procedures are considered not related if the said procedures would have been applied to the patients also in the absence of investigational device use/application.

In some particular cases the event may be not adequately assessed because information is insufficient or contradictory and/or the data cannot be verified or supplemented. The Sponsor and the Investigators will make the maximum effort to define and categorise the event and avoid these situations. Where the Sponsor remains uncertain about classifying the serious event, it should not exclude the relatedness and classify the event as “possible”.

Particular attention shall be given to the causality evaluation of USADE. The occurrence of an USADE could suggest that the clinical investigation places patients at increased risk of harm than was to be expected beforehand.

